## 9.7. Interventions and health care measures

Data on clinical interventions and health care measures will be collected as follows:

*Table 8: Items used to describe clinical interventions and health care measures*

Item	Description
Percutaneous endoscopic gastrostomy (PEG)	Y/N Date of provision (MM/YYYY)
Non-invasive ventilation (NIV)	Y/N Date of provision (MM/YYYY) Usage up to 8 hours per day Usage 8 to 16 hours per day Usage more than 16 hours per day
Invasive ventilation (IV)	Y/N Date of provision (MM/YYYY)
Provision of manual wheelchair (1)	Y/N Date of provision (MM/YYYY)
Provision of complex power wheelchair (1)	Y/N Date of provision (MM/YYYY)
Provision of augmented communication device (1)	Y/N Date of provision (MM/YYYY)
Provision of assistive technology (e. g. robotic arms), (1)	Y/N Date of provision (MM/YYYY)
Physical therapy (2)	Y/N Treatment units per week
Occupational therapy (2)	Y/N Treatment units per week
Speech and swallowing therapy (2)	Y/N Treatment units per week
Pharmacological therapy (3)	Riluzol, Y/N Symptomatic drugs, number of medicines

(1) Data will be obtained in a multi-center subset of up to 300 participants

(2) Data will be obtained in a single-center subset of up to 100 participants

(3) Data will be obtained in a multi-center subset of up to 200 participants

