## Study Synopsis

Tracking Number:

Protocol Title: Clinical characteristics, natural history, health care measures, and the frequency of genetic variants in the genes of SOD1, C9orf72, FUS and TARDBP in patients with sporadic and familial amyotrophic lateral sclerosis (ALS)

Version Number: 2.6

Study indication: Amyotrophic Lateral Sclerosis (ALS)

Study rationale: There is only limited data available on the frequency of genetic variants in patients with sporadic ALS (sALS) and familial ALS (fALS). In patients with sALS (patients without family history of ALS), genetic investigations do not belong to the standard of care. As a result, the patient's mutation status is commonly unknown. Even in patients with fALS (with known family history of ALS), screening for genetic mutations is not performed on a regular basis, due to lacking treatment options in the field of gene therapy. However, this paradigm is about to be changing as clinical trials on genetic medicines are ongoing and might result in the approval of new genetically investigated drugs in the future. This project is intended to investigate a large cohort of ALS patients on family history, clinical characteristics, health care measures and genetic variants in SOD1, C9orf72, FUS and TARDBP – the most commonly mutated genes in ALS. This cohort study will allow to determine the frequency of gene mutations in ALS patients in a real-world setting of ALS centers in Germany. Furthermore, the project shall enhance insights into potential differences between genetically defined cohorts by means of the course of disease and the provision of health care measures. The investigation of genetically distinct ALS cohorts is particularly relevant, as an improved understanding of the relationship between the genotype and the journey of disease is scientifically indispensable, in order to determine the therapeutic potential of future genetic therapies.

Objectives and Endpoints: Primary objective

- To identify the frequency of genetic variants in the genes of SOD1, C9orf72, FUS and TARDBP in patients with sALS and fALS

Secondary objectives

- To investigate the demographic and social characteristics
- To investigate the family history for ALS or FTD
- To investigate the clinical classification, functional deficits and progression

- To register interventions and health care measures including percutaneous endoscopic gastrostomy (PEG), ventilation therapy,

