- To register the provision with assistive technology devices, symptomatic pharmacotherapy and physical, occupational and speech therapy
- To investigate the clinical classification, functional deficits, disease progression and health care measures in a subset of ALS patients with pathogenic variants in the genes of SOD1 or C9orf72 as compared to ALS patients with no ALS-associated mutations in the investigated genes
- To register the values of serum concentration of neurofilament light chain (sNfL)
- To identify patient's treatment expectations towards ALS therapy using the Measure Your Medical Outcome Profile (MYMOP2)

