## 2. Introduction

### 2.1. Background

ALS is an adult-onset degenerative motor neuron disorder leading to progressive motor deficits and eventually to death within a few years (Brown et al. 2017). Currently, there is no effective disease modifying drug available. A distinction is made between sporadic and familial ALS (Kiernan et al. 2021). Sporadic ALS (sALS) refers to the occurrence of ALS in a single individual without known family history of ALS or frontotemporal dementia (FTD). Reportedly, population genetic studies in ALS found sALS in more than 90% of all ALS patients (Brenner et al. 2019, Kim et al. 2020, Volk et al. 2017, Zou et al. 2017). The term "familial ALS" (fALS) relates to the occurrence of ALS or FTD in several family members of a given trait. The definition of fALS encompasses positive cases of FTD as this neurodegenerative disorder may share common pathogenic pathways with ALS.

In patients with sALS, genetic tests for SOD1, C9orf72, TARDBP or other genes are not subject to standard care. The previous findings on the frequency of genetic variants in ALS-associated genes can be traced back to a few populations genetic studies of ALS (Volk et al., 2018). As a result, sALS patients and treating neurologists are commonly unaware of the patient's mutation status. Even in patients with positive or uncertain family history of ALS or FTD, screening for genetic mutations is not performed on a regular basis. Reportedly, ALS-associated genetic variants are mostly found in the genes of SOD1, C9orf72, FUS, and TARDP (Brenner et al. 2019, Kim et al. 2020, Volk et al. 2017, Zou et al. 2017). More specifically, mutations in SOD1 were found in 14.8% of patients with fALS and 1.2% of the sALS population. The disease is causing repeat expansions of the C9orf72 gene, among which 6.5% are identified of the total ALS cohort (34% of fALS, 5% of sALS) (Zou et al. 2017).

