Patients who refuse to be notified about study results will not be informed about the outcome of genetic analysis. This patient's directive explicitly includes pathogenic mutations that might be of diagnostic or therapeutic relevance. The patient's directive of notification of all genetic study results will include normal findings (no or benign variants) genetic, genetic variants of unknown significance and pathogenetic mutations (likely pathogenic or pathogenic genetic variants in the investigated genes of SOD1, C9orf72, FUS and TARDBP. Results of diagnostic relevance are defined as genetic variants being known to cause ALS or can increase the risk of ALS or can modify the phenotype of the disease including the progression rate. The finding of pathogenic variants can lead to the diagnosis of fALS although the disorder – given the negative family history of ALS – has prior been classified as sALS. The diagnostic relevance can extend to other family members as likely pathogenic or pathogenic mutations in the study at ALS genes might substantiate a genetic risk for ALS to first- and second-degree relatives of study participants. Therapeutic relevance is defined by the planning or performance of a phase 3 clinical trial, a planned or ongoing early access program or an expected approval of genetic medicine targeting one of the studied genes within the next 12 months. Currently, therapeutic relevance can be stated for mutations found in the SOD1 gene. Therapeutic relevance of C9orf72 and FUS can be expected within the next few years post-approval of this study protocol. The definition of diagnostic and therapeutic relevance and the scheme of notification of individual study results is provided in table 11.

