#### **12.3.5. Follow-up on study results with therapeutic relevance**

Therapeutic relevance is defined by the planning or performance of a phase 3 clinical trial, a planned or ongoing early access program or an expected approval of a genetic medicine targeting one of the studied genes within the next 12 months. The principal investigator and the genetic review board will analyze, review and interpret published information on the planning, beginning and completion of phase 3 clinical trials, early access programs or approvals of genetic medicines targeting one of the studied genes. The therapeutic residence will be defined as described at least every 12 months for 3 years after the beginning of the study. The extension of this review activity is of great scientific and medical value and will be subject of further investigations and related protocols.

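### Gene-targeted therapy and interventional-trial participation are neither recorded nor handled, so if SOD1 carriers are treated, the exploratory SOD1 versus no-mutation comparison over time cannot separate genotype from treatment

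*Combined protocol and SAP*

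**What the plan says.** **What is recorded.** For drugs, Table 8 (section 9.7) has one line: "Riluzol, Y/N Symptomatic drugs, number of medicines". A footnote limits it to a multi-center subset of up to 200 participants, and Table 1 marks it at V1 only.

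**What is compared.** The title announces "Clinical characteristics, natural history, health care measures, and the frequency of genetic variants". A secondary objective in the Synopsis looks at function, progression and health care measures in SOD1 or C9orf72 carriers "as compared to ALS patients with no ALS-associated mutations in the investigated genes". Section 11 applies this comparison to baseline characteristics and to changes over time. It names sex, age and intervention history as covariates and refers in general terms to potential confounders.

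**What is said about treatment.** Section 12.3.1 states: "Currently, therapeutic relevance can be stated for mutations found in the SOD1 gene". It adds: "Therapeutic relevance of C9orf72 and FUS can be expected within the next few years post-approval of this study protocol". Section 12.3.5 gives the definition, "Therapeutic relevance is defined by the planning or performance of a phase 3 clinical trial, a planned or ongoing early access program" (an expected approval within 12 months also counts), and has the status reviewed "at least every 12 months for 3 years after the beginning of the study". Section 12.3.2 says that counseling before entry covers gene-specific options that are available or in development. Against this, section 2.1 says: "Currently, there is no effective disease modifying drug available". Section 2.2 likewise says that no genetically defined treatment exists.

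**The concern.** The protocol follows, gene by gene, whether a targeted treatment is being tested or is close to approval, and its notification scheme can inform individual carriers of a therapeutically relevant result. It does not plan to record whether a participant then receives such a treatment or joins a trial.

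If some SOD1 carriers do, their later ALS-FRS, progression and sNfL values are pooled with those of untreated carriers. Gene-targeted exposure would fall on the carrier side only, so genotype and treatment would be confounded in the longitudinal comparison. A reader could not tell a slower disease course from a treated one. If the exposure data are not collected, no analysis choice at the end can restore them.

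**Working it through.** **1. Is there any item or rule that would identify exposure?**
- Tables 2–7, 9 and 10 cover demographics, social data, disease history, family history, classification, function with sNfL, MYMOP2 and genotype. None has a treatment or trial field. Table 1 schedules nothing further of this kind.
- Table 8 holds PEG, ventilation, devices, therapies and the drug line. Even with full coverage, that line gives riluzole yes/no and a count of unnamed symptomatic drugs, without dates.
- Sections 5.2, 5.3 and 7 do not mention gene-targeted drugs or concurrent trials. Sections 8.1 and 8.2 name no other drug source.
- Section 11 has no rule to exclude, censor, stratify or flag such participants. Intervention history is not defined there. Section 3.3 uses the term interventions for PEG and ventilation. Neither this covariate nor the general reference to confounders has a collected variable to work with.

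**2. How many carriers are involved?** The plan gives no sample-size calculation to reproduce, so the counts come from section 2.1: SOD1 14.8% of fALS and 1.2% of sALS; C9orf72 34% of fALS, 5% of sALS and 6.5% overall; sALS more than 90%.
- Lower fALS share f, solved from the C9orf72 figures: 6.5 = 34f + 5(1 − f), so f = 1.5/29 = 5.2%. Upper share: 10%.
- SOD1 share = 14.8%·f + 1.2%·(1 − f) = 1.90% to 2.56%.
- Of 2,000 planned: 38.1 to 51.2. Of 1,000 completers (section 5.1 expects more than 1,000): 19.0 to 25.6, assuming that carriers complete at the average rate.
- C9orf72 share = 34%·f + 5%·(1 − f) = 6.5% to 7.9%, or 65 to 79 of 1,000 completers.

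**3. Why can the two not be separated?** Let D be the carrier-minus-comparator difference in monthly ALS-FRS loss without treatment, q the treated share of carriers, and τ the mean slowing per treated carrier. Then

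observed difference = D − q·τ.

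Without an exposure variable q is unknown. Purely as an illustration with assumed values, an observed 0.15 points per month fits D = 0.30 with q = 50% and τ = 0.30 (0.30 − 0.15), and equally D = 0.15 with q = 0. The documents give none of D, q or τ, so this shows non-identifiability, not a bias estimate.

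**4. What would an unexposed-only analysis cost in precision?** Assume that 25% or 50% of SOD1 completers contribute no unexposed follow-up, with equal SDs. The comparator n0 is 1,000 − (19.0 + 65.0) = 916, or 1,000 − (25.6 + 79.0) = 895. FUS and TARDBP carriers are not subtracted, because no frequencies are given.
- Remaining SOD1 completers: 0.75 × 19.0 to 25.6 = 14.3 to 19.2; 0.50 × 19.0 to 25.6 = 9.5 to 12.8.
- SE ratio = √[1/(k·n1) + 1/n0] / √[1/n1 + 1/n0], where k is the share remaining: 1.15 for k = 0.75 and 1.40–1.41 for k = 0.50.
- If trial participation removed the same share of the comparator, the ratio would be √(1/k) = 1.15 or 1.41, so the large comparator group hardly matters.

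**The case against.** The strongest case against runs as follows. This is an exploratory real-world registry with no formal hypothesis. Its objectives ask how genetic groups differ, not how untreated carriers would fare, and natural history stands in the title but not in the objectives, endpoints or section 11. An as-observed comparison is legitimate in that setting. Sections 2.1 and 2.2 deny that an effective or genetically defined treatment exists, and a planned phase 3 trial alone satisfies the definition of therapeutic relevance. Section 11 also leaves room to adjust for confounders.

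Most of this stands and limits the point. What does not stand is the adjustment argument, since no variable is collected for it. Nor does an as-observed analysis remove the need to say how much of the observed follow-up was treated.

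A reader might infer three stronger things that the documents do not support:
- **That treated carriers are in the cohort and the results are biased.** No participant is shown to be treated, and no uptake, effect or treated time is given.
- **That C9orf72 is affected to the same degree.** Current relevance is stated for SOD1 only. For C9orf72 it is expected within a few years, while each participant is followed for about 12 months (section 4.1).
- **That nothing links individual participants to therapeutic relevance.** The notification directive in section 12.3.1 and the counseling path in Table 11 do so. They do not record exposure.

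The eCRF is not among the documents and may hold fields that the protocol does not list.

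**Conclusion.** The gap is real and worth closing, though it is conditional and limited to one exploratory analysis. The planned items and section 11 neither record nor handle gene-targeted therapy or interventional-trial participation, although the protocol makes such exposure foreseeable for SOD1. If SOD1 carriers are exposed before or during follow-up, the SOD1 versus no-mutation comparison of changes over time cannot separate genotype from treatment. Baseline comparisons are touched only by exposure before V1. The frequency of variants, the primary endpoint, is unaffected.

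The group at issue is small, so a few treated carriers could matter. The counts rest on the section 2.1 frequencies, an fALS share of 5.2–10% and, for completers, average completion among carriers. Neither the size nor the direction of any distortion can be derived.

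**What to change.** **Data.** Add two items to Tables 1 and 8 at V1, V2 and V3, taken from medical records (a source that section 8.1 already uses for interventions):
- Gene-targeted therapy Y/N, start and stop (MM/YYYY).
- Interventional trial participation Y/N, start and stop (MM/YYYY).

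Ask all participants, so that trial exposure is recorded alike in both groups. Concealing carrier status is not the reason: note 2 to Table 1 already gives SOD1 participants a distinct schedule.

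**Analysis.** In section 11, report the number exposed and the exposed months per group. Give the longitudinal genetic-subset comparison as observed and, as a sensitivity analysis, restricted to unexposed follow-up. Define unexposed as visits before the first recorded start of gene-targeted therapy or of an interventional trial, applied alike in both groups. A participant first exposed between V2 and V3 then contributes V1–V2 only, stated as an exception to the complete-case rule.

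**Cost.** At most 2,000 × 3 = 6,000 visit forms and 12,000 yes/no answers. With 1,000 at V3 and an assumed 1,000–2,000 at V2, it is 4,000–5,000 forms and 8,000–10,000 answers. Dates are needed only for the exposed, and nobody's care changes. The downsides are:
- Treatment or trials outside the site may be under-recorded.
- The unexposed SOD1 group is smaller and its estimate less precise.
- Stopping at treatment start may be informative, so the restricted analysis is not a clean estimate of untreated course either.
- Trial participation does not show what was received.

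**If the items are not added,** state as a limitation that the comparison cannot separate disease course from gene-targeted treatment.

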## 9.8. Patient's expectations towards ALS therapy

Treatment expectations will be assessed by the Measure Yourself Medical Outcome Profile (MYMOP2, Hermann et al., 2014, Monnery et al., 2018, Ishaque et al., 2019). The MYMOP is a brief, patient-generated, problem-specific questionnaire, which requires participants to qualify – and by that means prioritize – bothersome symptoms or impairments. The MYMOP consists of four questions and is a brief, patient-generated, problem-specific questionnaire. The first two questions require participants to specify symptoms that concern them most. Sub-

sequently, participants evaluate the severity of this symptom on a 7-point Likert scale (e.g., weakness of the right leg could score 0 for “as good as it could be” to 6 for “as bad as it could be”). The third question of the questionnaire uses the same 7-point Likert scale to assess whether the symptom is limiting or preventing a daily activity (such as walking). In the fourth question participants rate their general well-being. All domains (symptom severity, restriction of activity, and general well-being) can be analyzed individually or as a total score.

*Table 9: Items used to describe patient's expectations towards ALS therapy*

Item	Description
Symptom 1	Qualitative description Likert scale 0-6
Symptom 2	Qualitative description Likert scale 0-6
Activity	Qualitative description Likert scale 0-6
Well-Being	Likert scale 0-6

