#### **3.3. Additional objectives**

The additional objectives of this study are as follows:

- To investigate the demographic and social characteristics
- To investigate the family history for ALS or FTD
- To investigate the clinical classification, functional deficits, disease progression and health care measures in a subset of ALS patients with pathogenic variants in the genes of SOD1

or C9orf72 as compared to ALS patients with no ALS-associated mutations in the investigated genes

- To register available data on serum concentration of neurofilament light chain (sNfL)
- To register the history of interventions and health care measures including percutaneous endoscopic gastrostomy (PEG) and ventilation therapy
- To register the provision with assistive technology devices, symptomatic pharmacotherapy and physical, occupational and speech therapy
- To identify patient's treatment expectations towards ALS therapy using the Measure Your Medical Outcome Profile (MYMOP2)

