##### *Patient's expectations towards ALS therapy*

- Measure Your Medical Outcome Profile (MYMOP2)

This evaluation is exploratory. There is no formal hypothesis that is tested.

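### The objective on treatment expectations rests only on MYMOP2, whose scores record symptoms, activity limitation and well-being; relabel it and limit the conclusions

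*Combined protocol and SAP*

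**What the plan says.** Section 3.3 lists as an additional objective: "To identify patient's treatment expectations towards ALS therapy using the Measure Your Medical Outcome Profile (MYMOP2"). The Synopsis has the same aim among its secondary objectives. In the Synopsis and in Section 3.4.2, MYMOP2 is the only endpoint under the heading on expectations. Table 1 schedules it at V1, V2 and V3 under a treatment-expectation heading.

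Section 9.8 opens with "Treatment expectations will be assessed by the Measure Yourself Medical Outcome Profile" and then describes the questionnaire. It notes that "The MYMOP consists of four questions", and closes with "All domains (symptom severity, restriction of activity, and general well-being) can be analyzed individually or as a total score".

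Table 9, captioned as describing expectations, has four rows: Symptom 1, Symptom 2, Activity and Well-Being. Each is scored 0 to 6. The first three also carry a free-text description.

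Section 11 treats MYMOP as metric data for the t-test, alongside ALS-FRS. It applies this to comparisons of genetic subsets, both at baseline and for change over time. It also plans a standardised mean difference (SMD) of within-subject change for each measure.

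**The concern.** The label and the measurement differ. The plan names the construct as what patients expect of ALS treatment, but the instrument it describes rates how the patient is doing.

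Section 11 compares SOD1 and C9orf72 carriers with patients in whom no mutation was found in the tested genes. If a score difference or a 12-month change is reported under the protocol's own heading, it will carry an expectation label although it shows burden or well-being. Section 2.1 describes ALS as progressive, so scores may worsen over follow-up whatever patients expect of therapy. The covariates named in Section 11 (sex, age, intervention history) cannot turn a burden score into an expectation score.

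The study is motivated by possible genetic therapies, so a statement about patients' expectations by genotype would attract attention. It should not rest on a heading.

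**Working it through.** No arithmetic figure in the plan depends on MYMOP2. The check sets the stated construct beside the items, then looks for any other source of expectation data.

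**Step 1: the items, as Section 9.8 and Table 9 describe them**

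| Item | What the patient gives | Asks about therapy or expected benefit? |
|---|---|---|
| Symptom 1 | Free text; severity 0–6 | No |
| Symptom 2 | Free text; severity 0–6 | No |
| Activity | Free text; degree of limitation 0–6 | No |
| Well-being | Rating 0–6 | No |

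For the first two items the text says "The first two questions require participants to specify symptoms that concern them most", after which "participants evaluate the severity of this symptom on a 7-point Likert scale". The anchors run from 0 (best) to 6 (worst).

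**Step 2: count.** Items on expectation: 0 of 4. Named domains on expectation: 0 of 3.

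**Step 3: other sources.** I looked for a further expectation item, or a rule deriving expectations from MYMOP2, in the Synopsis endpoints and key assessments, Section 3.4.2, Table 1, Sections 8.1 and 8.2, and Section 11. There is none. Sections 8.1 and 8.2 list MYMOP simply as a self-assessment scale next to ALS-FRS.

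**Step 4: what the planned analysis estimates.** The t-test and the SMD of change use the scores. Two patients with the same hopes for treatment but different symptom severity will score differently. Two with opposite hopes but the same symptoms, limitation and well-being will score the same. A difference in mean score therefore identifies burden and well-being only.

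**Step 5: the free text.** Three of the four items record it, and Section 9.8 says the questionnaire leads patients to set priorities among their problems. This is the only link to what patients might want treated. Section 11 promises descriptive statistics, including percentages, for each assessment. It gives no categories, coding rule or table for free text, and Section 9.8 speaks only of analysing domains or a total score.

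**The case against.** The strongest defence is that MYMOP2 is more than its score. The endpoint is the instrument, and the free-text entries show which problems patients put first, a plausible though indirect sign of what they want therapy to address. This stands in part. A reader might infer that the data can say nothing relevant to the objective, and the documents do not support that. They support a narrower statement: the scores do not measure expectations, and the free text could indicate priorities but has no specified analysis. Even a well-analysed list of priorities would show what matters most to patients, not what they think treatment will achieve.

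A reader might also take all four items to be ratings of current severity. Section 9.8 applies severity to the symptoms only; the third item rates limitation and the fourth well-being, and no time frame is given.

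Thirdly, no sentence in the protocol says that a rise in score will be read as a change in expectation. The domains are named openly, and the objective names its instrument. That is correct: misreporting is a risk created by the headings, not a stated intention. The risk remains, because the plan provides no other result under the expectation heading.

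Finally, the amount of follow-up is uncertain. In Table 1 the V2 and V3 entries for MYMOP2 carry the footnote on more frequent collection in SOD1 patients, but the footnote's details concern sNfL and ALS-FRS. How much longitudinal MYMOP2 data will exist outside the SOD1 group is unclear. The mismatch applies at baseline as well, so the point does not depend on this.

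**Conclusion.** The point holds in limited form. By the protocol's own description, MYMOP2 yields symptom severity, activity limitation and well-being. It is the only source for the objective on expectations, and none of its 4 items asks about therapy. The planned score comparisons by genetic group and over time cannot be interpreted as comparisons of expectations.

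The consequence is confined to one additional, exploratory objective with no formal hypothesis. The frequency of variants in the four genes, which is the primary objective, is untouched. The MYMOP2 data remain usable for what they measure.

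The conclusion assumes that Section 9.8 and Table 9 describe the whole questionnaire as used; nothing is drawn from outside knowledge of MYMOP2. A reader might infer that a direct question on expected benefit has to be added. The documents do not require it: relabelling resolves the mismatch, and a question added now would be missing for anyone already past V1.

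**What to change.** 1. Relabel throughout as patient-prioritised symptoms, activity limitation and well-being (MYMOP2). The places are the Synopsis (objective, endpoint, key assessments), the Table 1 heading, Sections 3.3 and 3.4.2, the heading and opening sentence of Section 9.8, and the caption of Table 9 with its entry in the list of tables. The questionnaire's name, which varies between sections, can be made uniform in the same edit.
2. State in Section 11 that conclusions from MYMOP2 scores are limited to burden and well-being, and that differences or changes in score will not be interpreted as differences in treatment expectations.
3. Add to Section 11 a descriptive table of the baseline free-text symptoms and activities, presented as patient priorities, by genetic group (SOD1, C9orf72, no mutation in the tested genes). Fix the categories in advance and code the entries without sight of the genetic result.

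Cost: items 1 and 2 are wording only and apply to data already collected. Item 3 needs no new assessment, but it does need coding. With three free-text fields per subject and about 2,000 subjects, that is at most 3 × 2,000 = 6,000 short entries at V1, and fewer where fields are blank or subjects fall outside the compared groups.
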